1.4. AL002 Dosage Determination

In this Phase 2 study, eligible participants with Early AD (Refer to Section 1.5 for definition of Early AD) will each receive 1 of the following 4 treatments: placebo, 15 mg/kg AL002, 40 mg/kg AL002, or 60 mg/kg AL002.

The doses selected for this Phase 2 study are based on the clinical experience during the dose-escalation Phase 1 study conducted in healthy volunteers (Study AL002-1). Population pharmacokinetic and pharmacodynamic modeling has been performed on the preliminary data from Study AL002-1. Dose-response outputs from the model support dosing with 15 mg/kg, 40 mg/kg, and 60 mg/kg in the Phase 2 study.

Based on simulations of serum concentrations of AL002, the 75th percentile for 15 mg/kg is lower than the 25th percentile for 40 mg/kg. The 40 mg/kg and 60 mg/kg simulations are closer together with the 75th percentile from 40 mg/kg being close to the median for 60 mg/kg. Simulations of concentrations of AL002 in the CSF produced similar results.

Based on simulations of the target engagement marker sTREM2 in CSF, the 75th percentile for 15 mg/kg is slightly higher than the 25th percentile for 40 mg/kg. The simulations for 40 mg/kg and 60 mg/kg suggest that a similar effect on sTREM2 may be seen for these 2 doses. Based on these simulations sTREM2, the predication is that downstream biological activity will be similar for the 40 mg/kg and 60 mg/kg dose levels, with a somewhat higher likelihood of activity for the highest dose level at 60 mg/kg.

A 15 mg/kg dose is considered a low dose, but one that has an effect on sTREM2 in the brain and that could still provide benefit. The 40 mg/kg dose is currently predicted to provide a similar effect on sTREM2 compared to the 60 mg/kg dose, but with lower exposure. The 60 mg/kg dose will provide a higher exposure and PK/PD data in participants should 40 mg/kg not provide sufficient clinical benefit. Testing these doses in the current Phase 2 study is expected to provide adequate information for selecting the dose for subsequent Phase 3 studies.

PK in serum of the healthy volunteers of Study AL002-1 is characterized by a terminal half-life of 9.0 days at an IV dose of 15 mg/kg and 9.1 days at an IV dose of 60 mg/kg. C_{max} and total AUC (AUC $_{inf}$) were generally dose proportional. For additional information regarding PK data in these cohorts, please refer to Section 5 of the IB.

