#### 3.2 Randomization

Participants in Part 1 (approximately 40 participants total) will be randomly assigned on or prior to the Predose Baseline visit (if applicable), or on or prior to the Day 1 visit (if there is no Predose Baseline visit), by stratification on APOE e4 status (e4 carrier vs non-e4 carrier) to receive 15 mg/kg AL002, 40 mg/kg AL002, 60 mg/kg AL002, or placebo in an overall 1:1:1:1 allocation ratio. Participants in Part 2 (approximately 288 participants total) will also be randomly assigned on or prior to the Predose Baseline visit (if applicable) or on or prior to the Day 1 (if there is no Predose Baseline visit) by stratification on APOE e4 status (e4 carrier vs non-e4 carrier) to receive 15 mg/kg AL002, 40 mg/kg AL002, 60 mg/kg AL002, or placebo, using a 1:1:1:1 allocation ratio. An interactive web response system will be used to administer the randomization schedule. Further specific details will be described in the randomization specifications.

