#### 5.3.4 Pharmacokinetic (PK) Set

The PK Set will include all participants in the ATS that received AL002, had at least one post-dose measurable concentration, and are non-e4/e4. The PK Set will only be used for concentration descriptive summary.

All PK summaries using the PK Set will group participants according to the actual treatment received and follow the same rules as described above in the ATS (Section 5.2).

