#### 7.6 Pharmacokinetic Endpoints

All PK summaries will be performed on the PK Set. AL002 concentration will be summarized by analysis visit (refer to Table 7-13 and Table 7-14 for analysis visit window definition) and nominal time point as collected, separately for serum and CSF PK. Summary statistics will include coefficient of variation (CV) as percent and geometric mean in addition to the descriptive statistics (excluding Q1 and Q3) described in Section 7.1.

AL002 mean (+ SD) concentration-time data will be plotted (linear and semi-log) by elapsed time since the first study drug administration (in hours, i.e., (time of collection – time of the first study drug administration + 1) and treatment group for the first dose, separately for serum and CSF PK. The same plot (linear and semi-log) will be repeated for the seventh dose.

AL002 mean (+ SD) trough concentration-time data will also be plotted (linear) by elapsed time since the first study drug administration (in nominal weeks) by ADA group (positive and negative), separately for serum and CSF PK. In each ADA group, all treatment groups will be combined. The ADA positive group includes all participants who had at least one positive ADA result any time post-baseline. The ADA negative group includes all participants whose ADA results were all negative post-baseline. Participants who did not have any ADA post-baseline result will be excluded from this plot.

For the summaries and mean plots of AL002 concentrations, concentrations that are below LLOQ (below the limit of quantifications (BLQs)) before the first measurable concentrations on Study Day 1 will be set to zero, and all BLQs after Study Day 1 will be set to missing. The rules specified in Section 7.1.4.1.1 do not apply to PK.

Potential correlations of serum and/or CSF PK data with demographics, safety (including QT changes), efficacy, and PD measures may be explored, as data allow. Additional modeling, including population PK analysis and/or PK/PD analyses to characterize these correlations may be performed. These additional analyses of PK/PD data will be covered in a separate analysis plan and reported separately from the CSR.

The AL002 concentration data will be listed for the ATS.

Protocol No. AL002-2 Last Revision Date: 12 Aug 2025

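### The only specified display relating ADA status to exposure pools 15, 40 and 60 mg/kg, so if ADA incidence differs by dose it could show a false ADA effect or hide a real one

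*SAP*

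**What the plan says.** SAP 7.6 plans a linear plot of mean (+SD) trough against nominal week by ADA group, separately for serum and CSF. It states that "In each ADA group, all treatment groups will be combined". On group membership, "The ADA positive group includes all participants who had at least one positive ADA result any time post-baseline"; the negative group has only negative post-baseline results.

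The population follows from SAP 5.3.4: "The PK Set will include all participants in the ATS that received AL002, had at least one post-dose measurable concentration, and are non-e4/e4". Placebo therefore drops out, and the pool is the three active doses. The same section sets a general rule, "All PK summaries using the PK Set will group participants according to the actual treatment received", from which this plot is a specific departure. The other concentration-time plots in 7.6 are by treatment group but not by ADA status.

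SAP Table 2-1 lists the effect of immunogenicity on PK as an objective, and protocol 8.3.4 also names the impact of ADAs on PK findings. SAP 7.8.1 tabulates ADA results and titres by visit and treatment group, without PK.

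On exposure, protocol 1.4 reports that in the healthy volunteers of the Phase 1 study Cmax and AUCinf "were generally dose proportional", with a "terminal half-life of 9.0 days at an IV dose of 15 mg/kg and 9.1 days at an IV dose of 60 mg/kg". In simulated serum concentrations, "the 75th percentile for 15 mg/kg is lower than the 25th percentile for 40 mg/kg".

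**The concern.** ADA status arises after randomisation, so equal allocation to the doses does not balance dose between the ADA groups. If exposure rises with dose and ADA-positives are drawn unevenly from the three arms, the two pooled mean lines differ for a reason unrelated to ADA. A drug-clearing ADA response could also be masked if ADAs were more frequent at the higher doses.

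This is the only specified output that sets ADA status against concentration. A reader of the study report would therefore have no planned summary with which to separate the two explanations.

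**Working it through.** The plan attaches no sample size, estimate or test to this plot, so there is no stated figure to reproduce.

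**Inputs**
- Doses of 15, 40 and 60 mg/kg with equal allocation (SAP 3.2), hence 60/15 = 4.0.
- Trough proportional to dose: an assumption, carried over from Cmax, AUCinf and the similar half-lives in protocol 1.4.
- ADA incidence: not in the documents. Assumed 20% overall, with the split across doses varied.

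**1. Shift in the mean with no true ADA effect**

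The ADA-positive mean is the sum of share × dose. The all-participant mean is (15 + 40 + 60)/3 = 38.33. The ADA-negative mean is (38.33 − 0.2 × positive mean)/0.8.

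| ADA-positive split, 15/40/60 | Implied incidence by dose | Positive mean | Negative mean | Ratio |
|---|---|---|---|---|
| Equal thirds | 20/20/20% | 38.33 | 38.33 | 1.00 |
| 45/30/25% | 27/18/15% | 33.75 | 39.48 | 0.855 |
| 60/20/20% | 36/12/12% | 29.00 | 40.67 | 0.713 |
| 20/30/50% | 12/18/30% | 45.00 | 36.67 | 1.227 |

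For the second row, 0.45 × 15 + 0.30 × 40 + 0.25 × 60 = 33.75, and (38.33 − 6.75)/0.8 = 39.48. Implied incidence is 3 × 0.2 × share.

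**2. A true within-dose reduction of 30%**

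The pooled ratio is 0.70 times the ratio above. The last row shows 0.70 × 1.227 = 0.86 and the third shows 0.70 × 0.713 = 0.50. With a steeper assumed gradient of 5/15/30% by dose:
- positive mean without effect: (0.05 × 15 + 0.15 × 40 + 0.30 × 60)/0.50 = 49.5, and × 0.70 = 34.65
- negative mean: (0.95 × 15 + 0.85 × 40 + 0.70 × 60)/2.50 = 36.1
- ratio: 34.65/36.1 = 0.96, so the reduction is almost hidden.

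**3. Equal incidence**

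The mean does not shift, but the SD does. The between-dose variance of 15, 40 and 60 about 38.33 is 338.9. A within-dose CV of c adds c² × (15² + 40² + 60²)/3 = c² × 1808.3. For c = 0.50, √(338.9 + 452.1)/38.33 = 0.73. For c = 0.30 the pooled CV is 0.58.

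**4. When the dose spread appears**

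Mono-exponential superposition with a 9-day half-life and 28-day dosing carries over f = 2^(−28/9) = 0.116 per interval. Using the titration in SAP Table 3-1, and dropping a common factor:

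| Trough | 15 mg/kg arm | 60 mg/kg arm | Ratio |
|---|---|---|---|
| Week 4 | 15.00 | 15.00 | 1.0 |
| Week 8 | 16.74 | 41.74 | 2.5 |
| Week 12 | 16.94 | 64.83 | 3.8 |
| Week 16 | 16.96 | 67.50 | 4.0 |

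For titrated participants, dose mixing cannot affect the Week 4 trough and has nearly its full effect from the trough after the third dose.

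**5. After the change**

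Within a dose group, dose cancels and the ratio equals the true effect: 1.00 with none, 0.70 with a 30% reduction. Dose-normalised troughs give the same under proportionality, but only with a suitable divisor. At Week 8, dividing the 60 mg/kg arm by its assigned dose gives 41.74/60 = 0.70, against 16.74/15 = 1.12 in the 15 mg/kg arm. That gap comes purely from titration.

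**The case against.** The strongest reply is that the bias is conditional. A reader might infer from the pooling alone that any ADA effect on trough is necessarily confounded with dose. The documents do not support that: neither gives ADA incidence in this trial, overall or by dose, and equal incidence gives a ratio of exactly 1.00. This part stands, and the splits above are illustrations only.

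Two further stronger readings also fail. One is that the protocol establishes dose-proportional troughs. It speaks of Cmax and AUCinf in healthy volunteers; extending this to multiple-dose troughs in Early AD, and to CSF, is an inference that the similar half-lives make plausible. The other is that a four-fold spread runs across the whole plot, which titration rules out.

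It can also be said that other outputs help. The ADA tables by treatment group would reveal an imbalance, and the listings of concentrations and ADA results would allow a check by dose. But the tables do not correct the plot, and a listing is not a summary. The PK modelling allowed in SAP 7.6 is optional, does not name ADA, and would be reported outside the study report.

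Finally, splitting by dose makes small cells. At about 82 per arm, incidence of 5% to 10% leaves roughly 4 to 8 ADA-positives per dose (82 × 0.05 = 4.1; 82 × 0.10 = 8.2). There would be fewer at late visits and in CSF, where lumbar puncture is optional in Part 2. This stands, and it shapes the fix.

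**Conclusion.** The point holds in conditional form. As specified, the plot cannot distinguish an ADA effect on trough from a difference in dose mix, and no other specified output fills the gap. If incidence varies with dose, false ratios of about 0.71 to 1.23 are possible under the assumed splits at 20% overall incidence, and a real reduction can be largely masked. If incidence is equal, the cost is only wider SD bars. These sizes rest on assumed incidences, equal numbers per dose and troughs proportional to dose, and for titrated participants they apply mainly from the trough after the third dose.

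A reader might go on to infer that the trial's efficacy or safety conclusions are affected. They are not: this is one descriptive display, SAP 7.8 labels the immunogenicity analyses exploratory, and no test or decision depends on it. The change is desirable and low in priority.

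**What to change.** In SAP 7.6, replace the pooled display with trough by ADA status within each actual-treatment group, for serum and CSF, with a matching summary table and n shown at each visit. Where cells are too small for a mean and SD, show individual values. Alternatively, show dose-normalised trough, defined as concentration divided by the last dose actually received in mg/kg and limited to visits after titration is complete. If a pooled plot is kept, label it secondary and state the dose mix in each ADA group.

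The cost is SAP wording and a few extra panels, with no new data collection. The price is sparse cells, chiefly for CSF and late visits; showing n makes that visible.

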#### 7.7 Exploratory PD Biomarker Endpoints

All PD biomarker analyses will be performed on the FAS. The key biomarker objectives are listed below:

- *PD assessment*: Assess the treatment effect in AL002 vs. placebo for the CFB in biomarker levels
- Correlation with CDR-SB: Assess the treatment-related association between CFB in biomarker levels (fluid and imaging) and CFB in CDR-SB.
- Baseline plasma pTau217 as disease staging variable: Assess treatment effect in AL002 vs. placebo in CFB in COAs and plasma biomarkers with baseline plasma pTau217 as a disease staging variable.

Biomarkers will be bucketed into subset 1 and subset 2 based on the analysis scope, with more analyses planned for subset 1 compared to subset 2. Biomarker subsets are listed in Table 7-25. The analysis scopes are listed in Table 7-26, Table 7-27, and Table 7-28 for the key biomarker objectives.

**Table 7-25. Biomarker Subsets** 

Biomarker Type	Subset 1	Subset 2
CSF	
 
sTREM2 (target engagement)
 
IL1RA (TREM2 engagement)
 
Osteopontin (TREM2 engagement)
 
pTau217 (amyloid and Tau)
 
MTBR Tau-243 (amyloid and Tau)
 
Aβ42/40 (amyloid)
 
GFAP (neuroinflammation and neurodegeneration)
 
CSF1R (microglial survival and proliferation)
 
NfL (neurodegeneration)
 
	
 
YKL-40 (neuroinflammation)
 
Total Tau (neurodegeneration)
 
IL-6 (neuroinflammation)
 
s100b (neuroinflammation)
 
Neurogranin (synapse loss)
 
NPTX2 (synapse degeneration)
 
SNAP25 (synapse degeneration)
 
pTau181 (amyloid)
 

Plasma	
 
IL1RA (TREM2 engagement)
 
pTau217 (amyloid and Tau)
 
Aβ42/40 (amyloid)
 
GFAP (neuroinflammation and neurodegeneration)
 
NfL (neurodegeneration)
 
	• pTau181 (amyloid)
Amyloid PET (normalized to whole cerebellum)	
 
Composite ROIs:
 
Global cortical average, SUVR measure
 
Global, centiloids measure
 
	
 
Roll-up ROIs, SUVR         measure:         
 
Frontal
 
Lateral temporal
 
Lateral parietal
 
Cingulate
 
Lateral occipital
 
 
 

# Statistical Analysis Plan Protocol No. AL002-2

Last Revision Date: 12 Aug 2025

Biomarker Type	Subset 1	Subset 2
Tau PET (normalized to cortical grey matter of cerebellum)	
 
Roll-up ROIs, SUVR measure:         
 
Medial temporal
 
Temporal
 
Frontal
 
Cingulate
 
Parietal
 
Occipital
 
Whole cortical gray matter
 
Temporoparietal
 
 
 
Rowe metatemporal composite ROI, SUVR measure
 
Jack metatemporal composite ROI, SUVR measure
 
	
MRI	
 
Volumetric parameters:
 
Temporal cortex
 
Parietal cortex
 
Whole brain
 
Hippocampus
 
Ventricles
 
	

CSF = cerebrospinal fluid; MRI = magnetic resonance imaging; PET = positron emission tomography; ROI = region of interest; SUVR = standardized uptake value ratio.

Table 7-26. Analysis Scope for PD Assessment Objective

Analysis Scope	Endpoint	Analysis Method
Assess treatment effect of AL002 doses vs. placebo in the FAS	
 
CFB to scheduled post-baseline visits (see Section 7.7.1.1) in plasma biomarker levels [subset 1 and subset 2]
 
CFB to week 6, 48, 72 in CSF biomarker levels [subset 1 and subset 2]
 
CFB to week 48 in amyloid PET [subset 1 and subset 2 parameters]
 
CFB to week 48 and 72 in Tau PET [subset 1 parameters] [a* and b*]
 
CFB to scheduled post-baseline visits (see Section 7.7.1.1) in MRI [subset 1 parameters]
 
	only subset 1 Tau PET parameters [table]  • Descriptive summaries (main estimand) [tables]

Protocol No. AL002-2 Last Revision Date: 12 Aug 2025

Analysis Scope	Endpoint	Analysis Method
Assess treatment effect of AL002 doses vs. placebo in subgroups defined by  • Baseline demographics: gender (male, female), age (< 65 years, ≥ 65 years), AD diagnosis (mild cognitive impairment (MCI), mild dementia (MD))  • APOE genotype: e4 carrier	• CFB to scheduled post-baseline visits in plasma biomarker levels	
 
Descriptive summaries (main estimand) for subset 1 plasma biomarkers [tables]
 
MMRM (main estimand)
 
APOE e4 carrier and non-e4-carrier subgroups [subset 1 only] [tables and figures]
 
Baseline demographics subgroups [subset 1 only] (tables only)
 

CFB = change from baseline; CSF = cerebrospinal fluid; MMRM = Mixed-Effects Model for Repeated Measures; MRI = magnetic resonance imaging; PD = pharmacodynamic; PET = positron emission tomography.

Table 7-27. Analysis Scope for Correlation with CDR-SB Objective

Analysis Scope	Endpoint		Analysis Method
Assess treatment-related association between CFB in biomarker levels (plasma, CSF, amyloid PET and Tau PET) and CFB in CDR-SB in the FAS set	CFB to scheduled post-baseline visits (week 48, 72, 96) in CDR-SB and subset 1 plasma biomarkers CFB to scheduled post-baseline visits (week 48, 72) in CDR-SB and subset 1 CSF biomarkers CFB to week 48 in CDR-SB and subset 1 amyloid PET parameters CFB to scheduled post-baseline visits (week 48, 72) in CDR-SB and subset 1 Tau PET parameters (a* and b*)	•	Group-level scatterplots of adjusted mean difference from placebo in CDR-SB and subset 1 biomarkers (plasma, CSF, amyloid PET and Tau PET) with Pearson and Spearman correlations at matching timepoints (main estimand). Adjusted correlative analyses [tables] of CFB in CDR-SB and subset 1 biomarkers (plasma, CSF, amyloid PET and Tau PET) at matching timepoints (main estimand)

CFB = change from baseline; CSF = cerebrospinal fluid; PET = positron emission tomography.

a\* True baseline: include participants with pre-dose Tau PET scan in the calculation for CFB.

 $b^*$  Redefined baseline: include participants with either pre-dose Tau PET if evaluable or 1st post-dose evaluable Tau PET scan if pre-dose PET scan is missing in the calculation for CFB.

*a\* True baseline*: include participants with pre-dose Tau PET scan in the calculation for CFB. *b\* Redefined baseline*: include participants with either pre-dose Tau PET if evaluable or 1st post-dose evaluable Tau PET scan if pre-dose PET scan is missing in the calculation for CFB.

Protocol No. AL002-2 Last Revision Date: 12 Aug 2025

Table 7-28. Analysis Scope for Baseline plasma pTau217 as Disease Staging Variable Objective

Analysis Scope	Endpoint	Analysis Method
Assess treatment effect in AL002 vs. Placebo in COAs and subset 1 plasma biomarkers with baseline plasma pTau217 as disease staging variable	
 
CFB to scheduled post-baseline visits (week 24, 48, 72, 96) in COAs (CDR-SB, ADAS-Cog13, ADCS-ADL-MCI, ADCOMS, modified iADRS, MMSE, and RBANS)
 
CFB to scheduled post-baseline visits (week 24, 48, 72, 96) in subset 1 plasma biomarkers
 
	
 
Subgroup analyses of CFB in COAs with subgroups based on baseline plasma pTau217 terciles (pMMRM, MMRM; main estimand) [tables and figures].
 
Subgroup analyses of CFB in subset 1 plasma biomarkers with subgroups based on baseline plasma pTau217 terciles (MMRM; main estimand) [tables and figures].
 

COAs = clinical outcome assessments; CFB = change from baseline.

#### 7.7.1 PD Assessment Objective

#### 7.7.1.1 FAS

For exploratory PD biomarkers (CSF, plasma, amyloid PET, Tau PET and volumetric MRI) listed in Table 7-25 [subsets 1 and 2] in the FAS, their visit values, change from baseline (CFB) and percent change from baseline (PCFB) for the main estimand will be summarized by treatment group over time (all visits) using descriptive statistics (Table 7-26).

Comparisons of CFB between AL002 dose groups vs. placebo will be explored for the main estimand using MMRM models (see Section 7.4.1.2) with treatment group, categorical visit, visit-by-treatment interaction, baseline biomarker, and APOE e4 status of e4 carrier vs. non-e4 carrier as fixed effects (Table 7-26). Treatment comparisons will be reported for specified visits as indicated below:

- Plasma biomarkers:
  - O AD-pathology (Aβ42/40, pTau217, MTBR-Tau243): week 12, 24, 48, 72 and 96
  - o AD-pathology (pTau181): week 16, 36, 60 and 84
  - o Target engagement (IL1RA): week 1, 2, 4, 6, 8, 12, 24, 36, 48, 72 and 96
  - o Neurodegeneration (NfL, GfAP): week 12, 24, 48, 72 and 96
- CSF biomarkers: week 6, 48 and 72
- Amyloid PET parameters: week 48
- Tau PET parameters: week 48 and 72
- Volumetric MRI parameters: week 48, 72 and 96

Additionally, the same analysis for the main estimand described above will be repeated with the following groups in the model: AL002 15 mg/kg group, AL002 40 and 60 mg/kg combined group, and placebo group. All statistics described above from fitting the MMRM model will be reported only for the AL002 40 and 60 mg/kg combined group (or its comparison to placebo).

For Tau PET parameters [subset 1] in Table 7-25, a sensitivity analysis (main estimand) will be conducted with similar descriptive summaries and MMRM models for the subset with redefined baseline (either pre-dose Tau PET if evaluable or the first post-dose evaluable Tau PET scan if pre-dose PET scan

Protocol No. AL002-2 Last Revision Date: 12 Aug 2025

is missing) (Table 7-26). A pMMRM model (main estimand) will be additionally conducted for both subsets of true baseline and redefined baseline (Table 7-26).

Given the limited sample size mapped to the Week 96 analysis visit for CSF, Amyloid PET and Tau PET, this visit will only be summarized descriptively and excluded from modelling (i.e., pMMRM and MMRM).

For amyloid PET centiloids measure, the number of participants with amyloid clearance (positive [centiloids ≥ 24.1] at baseline and negative [centiloids < 24.1] at week 48), and percentage with 95% CI (mid-p method), will be summarized by treatment group. Treatment comparison (vs. placebo) will be based on mid-p method.

Additional analyses based on supportive estimand will be provided for Tau PET ROIs [subset 1] for the subset with redefined baseline (descriptive summary, MMRM and pMMRM), and amyloid PET ROIs (descriptive summary and MMRM) [Table 7-25].

